4.6.1. Primary Endpoint

The primary endpoint is the composite of recurrent HF hospitalisations and CV death up to 52 weeks after randomisation, as confirmed by the CEC. If a subject is hospitalised due to HF and dies on the same day from any CV event, this would be counted as one event. All events up to the last known date or study day 375, whichever occurs first, will be considered for this endpoint.

The HF hospitalisation and CV death rates per 100 subject-years of follow-up as adjudicated by the CEC will be calculated by dividing the total number of HF hospitalisations and CV deaths by the subject-years of time on study (see section 4.2.14) of all subjects in each treatment group multiplied by 100.

Descriptive statistics will provide, per treatment group, the total number of events (HF hospitalisation and CV death), the number (%) of subjects with at least one event, and the number (%) of subjects with more than one event. The number of HF hospitalisations and CV deaths per subject and the time on study will be summarized as continuous and categorical variables. The HF hospitalisation and CV death rates per 100 subject-years will be reported by treatment group. The rate ratio (95% confidence interval [CI] and p-value) for this analysis will be analysed using a negative binomial model. Compared to the Poisson distribution, the negative binomial distribution allows for different individual tendencies (frailties) with respect to risk of repeat hospitalisation [7]; this overdispersion parameter will be the same across the treatment groups and randomisation strata. Varying follow-up times between the patients will be accounted for by including log-transformed time on study of each subject in years as intercept.

The negative binomial model will be adjusted for the following baseline covariates as measured at time of randomisation: sex, age at randomisation, HF aetiology (ischaemic/non-ischaemic/unknown), HF duration, and country. If there are too few subjects in some countries, country can be replaced for the adjustment by region as described in section 4.5.1. A sensitivity analysis will be performed using an unadjusted model.

SAS code to be used:

```
proc genmod data=dataset;
  class armcd (ref='placebo') sex hf_aetio hf_duration country;
  model count = armcd sex age hf_aetio hf_duration country / offset=logfu_dur
link=log dist=negbin type3;
  lsmeans armcd / exp cl diff;
  ods output lsmeans=lsm;
  ods output parameterestimates=est;

  *** Trt Comparison estimates;
  estimate 'Treated vs. placebo' armcd 1 -1 /exp alpha=0.05 ;

run;
```

logfu_duration is the log-transformed time on study of each subject in years.

Statistics will include the estimated rate of events per year, with 95% CI, per treatment group, and the estimated rate ratio between treatment groups, with 95% CI and p-value.

A descriptive graphical representation of the cumulative risk ratio (FCM vs placebo) over time will also be provided based on the calculated cumulative rate of events per 100 subjects over time in each treatment group.

Additionally, as the analysis of HF hospitalisations could be confounded by the competing risk of death, a confirmatory analysis will be performed on the FAS using the joint frailty model in order to analyse repeat hospitalisation data whilst accounting for the associated mortality rate [8]. The joint model allows for the modelling of the recurrent events and time to death simultaneously, including a common frailty term. This joint frailty model will give an estimate for the recurrent HF hospitalisation rate ratio which takes into account CV death as informative censoring and an estimate for the hazard ratio for CV death which takes into account the effect of recurrent hospitalisation on death. Both rates will be displayed with 95% CIs and p-values. For this analysis, if both a hospitalisation and a death occur on the same day, only the death will be counted.

The recurrent event process can be modelled by a random effects (frailty) proportional hazards model. In the presence of a dependent terminal event, the random effects are also incorporated into the model for the terminal events. The SAS code for this analysis will be based on [9]. General steps are described below:

- Generate a dataset with one row for each type of event including the following variables:
 - unique subject ID (*usubjid*),
 - covariates: categorical variables split in binary dummy variables,
 - treatment groups (*trt*): 1 for IV FCM and 0 for placebo
 - time to hospitalisation, censor or death (*timevar*), and
 - Event status (*event*): 0 for censoring, 1 for hospitalisation (recurrent event), and 2 for death (terminal event).

Note: the dataset may include several rows for the same subject. All subjects have to have a row with either censoring or death.

Note: the earliest from the hospitalisation start date or emergency start date will be used for time to hospitalisation, when applicable.

Note: prolonged index hospitalisations will have the start date for this analysis set to randomisation date.

- Calculate the quantiles of *timevar* separately for time to hospitalisation (*event* = 1) and for time to death (*event* = 2). The last interval for recurrent events and for death will then be prolonged up to the last censoring/death date within the dataset.
- Merge with the dataset generated in the first step.
- Calculate the duration and the indicator of event for recurrent event in each quantile interval:
 - For recurrent events, there are 10 variables dur_r_k , $k = 01, 02, \dots, 10$ with all zeroes for a row with a recurrent event and with length of follow-up within each interval for a row with censoring or death, and 10 variables $event_r_k$ for the indicator of the recurrent event happening in intervals 1 to 10, respectively;
 - For death, there are 10 variables dur_d_k filled with follow-up time within each interval for censoring or death and with all zeroes for rows with recurrent event. Variable $event_d_k$ takes the value of 1 if the event is death in the interval k , and 0 otherwise.

- Specify the initial values of the parameters in dataset INPAR. The piecewise constant baseline hazards are denoted by $r_{01}, r_{02}, \dots, r_{10}$ for recurrent events, and $h_{01}, h_{02}, \dots, h_{10}$ for terminal event.
- Use the following SAS code to get the parameter estimates. For simplicity, no covariates are included in the code below.

```
ods output ParameterEstimates= PAREST;

proc nlmixed data=all qpoints=x noad;
parms / data=INPAR;
bounds r01 r02 r03 r04 r05 r06 r07 r08 r09 r10 h01 h02 h03 h04 h05 h06
h07 h08 h09 h10 theta >=0;

/* baseline hazard and cum baseline hazard, recurrent events */
base_haz_r=r01*event_r1+r02*event_r2+r03*event_r3+r04* event_r4 +
r05*event_r5+r06*event_r6+r07*event_r7+r08*event_r8
+r09 * event_r9 + r10 * event_r10;

cum_base_haz_r=r01*dur_r1+r02*dur_r2+r03*dur_r3+r04*dur_r4 +
r05*dur_r5+r06*dur_r6+r07*dur_r7+r08*dur_r8+r09*dur_r9 +
r10 * dur_r10;

/* baseline hazard and cumulative baseline hazard for death */

base_haz_d=h01*event_d1+h02*event_d2+h03*event_d3+h04*event_d4 +
h05*event_d5+h06*event_d6+h07*event_d7+h08*event_d8+
h09 * event_d9 + h10 * event_d10;

cum_base_haz_d=h01 * dur_d1 + h02 * dur_d2 + h03 * dur_d3 +
h04 * dur_d4 + h05 * dur_d5 + h06 * dur_d6 + h07 * dur_d7 +
h08* dur_d8 +h09 * dur_d9 + h10 * dur_d10;

mu1= beta1 * trt + nu; /* for recurrent event */
mu2= alpha1 * trt + gamma * nu; /* for death event */
loglik1=-exp(mu1) * cum_base_haz_r;
loglik2=-exp(mu2) * cum_base_haz_d;

/*log likelihood for recurrent event */
if event=1 then loglik=log(base_haz_r) + mu1;

/*log likelihood for death */
if event=2 then loglik=loglik1 +log(base_haz_d)+mu2+loglik2;

/*log likelihood for censoring */
if event=0 then loglik=loglik1 + loglik2;

model timevar ~ general(loglik);
random nu ~ normal(log(1/sqrt(1+theta)),log(1+theta)) subject=usubjid
out=nu_est;
```

```
predict exp(loglik2) out=outs; /*estimated survival function of death event*/
predict exp(loglik1) out=cumh; /*estimated cum hazard of recurrent event*/
run;
```

- Take the natural exponential of the estimates to get the rate ratio and the hazard ratio with corresponding 95% confidence intervals.

In case the joint frailty model adjusted for baseline covariates does not converge, unadjusted model will be used instead.

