12.7 Efficacy Evaluations

12.7.1 Primary

The primary outcome is the composite of recurrent HF hospitalisations and CV death up to 52 weeks after randomisation.

The HF hospitalisation and CV death rates per 100 patient-years of follow-up as adjudicated by the CEC, will be calculated by dividing the total number of HF hospitalisations, and CV deaths by the total follow-up duration of all subjects in each group. The rate ratio (95% CI and p-value) for this analysis will be analysed using a negative binomial model. Compared to the Poisson distribution, the negative binomial

distribution allows for different individual tendencies (frailties) with respect to their risks of repeat hospitalisations [41].

The negative binomial model will be adjusted for the following baseline covariates: sex, age, HF aetiology (ischemic/non-ischemic), HF duration (newly diagnosed at Index hospitalisation/known documented HF prior to Index hospitalisation) and country. A sensitivity analyses will be performed using an unadjusted model.

The primary outcome analysis will be performed on the FAS will use the CEC adjudicated events. A sensitivity analysis will be performed on the PP population set.

Descriptive statistics will provide, per treatment group, the total number of events and the number (%) of subjects with at least one event.

A graphical representation of the estimated cumulative hazard rate will also be provided.

As the analysis of HF hospitalisations could be confounded by the competing risk of death, a confirmatory analysis will be performed on the FAS population set using the joint frailty model in order to analyse repeat hospitalisation rate whilst accounting for their associated mortality rate [42].

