4. STATISTICAL METHODS

4.1. Sample Size Justification

The recurrent HF hospitalisation and CV death rates in the control group were extrapolated as 0.9 events/year using the data from the EVEREST study [3] and as 0.61 events/year using the data from the ESC-HF study [4]. For this study, it is anticipated that approximately 35% of subjects will sustain either a CV death or at least one HF hospitalisation. It is also anticipated that 12% of subjects will sustain a CV death. Assuming that 50% of subjects who sustain a CV death will not undergo any prior HF hospitalisation and estimating the average number of HF hospitalisations per subject with at least one HF hospitalisation as 2, the number of events per 100 years of follow-up has been estimated as follows: 12 CV deaths + 2*(35-6) HF hospitalisations, which equates to approximately 70 events/100 years of follow-up for HF hospitalisations and CV death.

Concerning the event rate ratio, it is assumed that there will be a 30% reduction in HF hospitalisations for subjects allocated to FCM and that CV death rates will be similar between the FCM and placebo groups. It is therefore assumed that the rate ratio between FCM and placebo for the composite of recurrent HF hospitalisations and CV deaths will be approximately 25%.

The dispersion factor used in negative binomial regression is a measure of the mean-variance. There are currently insufficient data to estimate the negative binomial dispersion. For this sample size calculation, a dispersion factor (K) of 1 was assumed.

The sample size calculation was done in the software NCSS PASS-14 [5], using the sample size formula proposed by Zhu and Lakkis 2014 [6] to compare two negative binomial rates.

Assuming a rate of recurrent HF hospitalisation or CV death of 0.7 events/year in the placebo group, a total of 1,000 subjects (500 per study drug group) would be required to demonstrate a statistically significant rate ratio of 0.75 (i.e., 25% reduction of recurrent hospitalisations or deaths between the FCM and placebo groups) with a power of 80% and a 2-sided alpha of 0.05. Taking into account an expected 9% loss to follow-up, a sample size of 1,100 subjects (550 per treatment group) is planned.

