4.2.6. Subpopulations

Some analyses will be performed on the following subgroups:

- Hb level at baseline (< 12, ≥ 12 g/dL).
- Ferritin level at baseline by tertiles.
- Ferritin level at baseline (< 100 ng/mL, ≥ 100 ng/mL).
- TSAT category at baseline by tertiles.
- TSAT category at baseline (< 20%, ≥ 20%).
- Sex.
- Age by tertiles.
- Renal function at baseline defined as No CKD, CKD stages I and II, and CKD stages III, IV, or V at baseline medical history.
- Estimated glomerular filtration rate (eGFR) value at baseline by tertiles. The eGFR value at baseline will be calculated using the CKD-EPI formula and the baseline creatinine value.
- Ischaemic Aetiology of HF (ischaemic, non-ischaemic).
- NYHA at baseline (NYHA II, NYHA III, if applicable, i.e. if there are at least 10% of subjects by NYHA class and treatment group. NYHA I and IV not included).
- NT-pro BNP (pg/mL) or BNP (pg/mL) at baseline assigned to First tertile, Second tertile or Third tertile. Tertiles of NT-proBNP and BNP at baseline in FAS regardless of treatment group will be computed (for each parameter separately) and subjects will be assigned to these groups. In case subject has both values collected at baseline, NT-proBNP will be used and subject will be assigned according to computed NT-proBNP tertiles.
- Left ventricular ejection fraction (%) at baseline Left ventricular ejection fraction (LVEF) < 25%, ≥ 25% until < 40%, and ≥ 40% until < 50%
- Diagnosis of Heart Failure (newly diagnosed at index hospitalisation, known documented HF prior index hospitalisation).
- Subjects hospitalised for an episode of Acute Heart Failure in the previous 12 months prior Index Hospitalisation (yes, no).
- Creatinine at baseline by tertiles.

For subgroups defined by tertiles, tertiles will be computed on the FAS regardless of treatment group.

Additionally, following subgroups will be investigated for exploratory purposes:

- Geographical region (Latin America [Argentina, Brazil], Asia [Israel, Lebanon, Singapore], South and Eastern Europe [Italy, Croatia, Georgia, Romania, Ukraine], Central and Western Europe [Netherlands, Poland, United Kingdom, Spain, Sweden])
- Subjects with ARNI (yes, no)
- Subjects with ACE or ARB or ARNI, at least one of these groups (yes, no)
- Subjects with beta-blockers (yes, no)
- Subjects with Aldosterone Antagonists (yes, no)

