4.5.2. Baseline Disease Characteristics

Baseline disease characteristics will include:

- 1) History of cardiovascular risk factors:
 - any risk factor,
 - smoking,
 - hypertension,
 - dyslipidaemia,
 - diabetes mellitus,
 - atrial fibrillation,
 - myocardial infarction,
 - angina pectoris,
 - stroke,
 - coronary revascularization,
 - chronic kidney disease.
- 2) Index hospitalisation information (screening acute heart failure):
 - aetiology (ischaemic, non-ischaemic, unknown; if non-ischaemic, hypertensive, valvular, idiopathic, congenital, other),
 - AHF duration (newly diagnosed at Index hospitalisation, known documented HF prior to Index hospitalisation),
 - time since initial diagnosis to screening (years) as a continuous variable only for those with known HF prior to Index hospitalisation,
 - acute heart failure in the previous 12 months prior to Index hospitalisation (Yes/No),
 - number of hospitalisations in the 12 months prior to screening (for subjects with at least one previous hospitalisation before screening).
- 3) Symptoms and signs of heart failure at time of Index hospitalisation:
 - dyspnoea on exertion,
 - dyspnoea at rest while sitting,
 - orthopnoea and paroxysmal nocturnal dyspnoea,
 - peripheral oedema,
 - pulmonary congestion (crackles, rales),
 - liver enlargement,
 - presence of a third heart sound (S3 gallop),
 - jugular venous distension,
 - jugular venous measurement (cm).

- 4) Other baseline disease characteristics:
- left ventricular ejection fraction (%), left ventricular ejection fraction as categorical variable (<40%, 40-<50%, >=50%)
 - New York Heart Association Classification (Class I, II, III, IV),
 - baseline weight (kg), height (cm), BMI (kg/m²) and temperature (°C),
 - baseline laboratory data: haemoglobin (g/dL), haemoglobin as categorical variable (<10, 10-14, >14), anaemic/non-anaemic subjects (anaemic: adult males with Hb < 13 g/dL, adult females, non-pregnant with Hb <12), serum ferritin (ng/mL), serum ferritin as categorical variable (<100, 100-<300, >=300 ng/mL), transferrin saturation (%), transferrin saturation as categorical variable (<20%, >=20%), phosphorus (mg/dL), phosphorus as categorical variable (<1, 1-<2, 2-<2.5, 2.5-<4.5, >=4.5), creatinine (mg/dL), Brain natriuretic peptide (BNP) (pg/mL), N-terminal-probrain natriuretic peptide (NTproBNP) (pg/mL).

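### The primary negative binomial model adjusts only for minimisation factors; adding two baseline values already derived in SAP 4.2.6 would be a cheap and probably modest gain in precision

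*SAP*

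**What the plan says.** SAP 4.6.1 sets the primary model: "The negative binomial model will be adjusted for the following baseline covariates as measured at time of randomisation: sex, age at randomisation", then HF aetiology, HF duration and country, with region as a fallback for country. Protocol 12.7.1 agrees: "The negative binomial model will be adjusted for the following baseline covariates: sex, age, HF aetiology (ischemic/non-ischemic", then HF duration and country. SAP 2.2 lists sex, age group, aetiology, HF duration, country and centre as the minimisation factors, so every model covariate is one of these and only centre is dropped. The one alternative covariate set for the primary model is no covariates.

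Two further baseline values are available. SAP 4.5.2 lists "acute heart failure in the previous 12 months prior to Index hospitalisation (Yes/No" among the baseline characteristics. BNP or NT-proBNP is an entry criterion (Protocol 5.2), and the qualifying value goes into the eCRF (Protocol 9.2.5.1). SAP 4.2.6 uses both as subgroup factors: "Subjects hospitalised for an episode of Acute Heart Failure in the previous 12 months prior Index Hospitalisation (yes, no", and tertiles computed separately for each peptide, with NT-proBNP taking precedence when a subject has both. SAP 4.6.3 then enters each subgroup variable in its own exploratory model with a treatment interaction. Neither value is a main effect in the primary or secondary models.

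**The concern.** An AHF admission in the previous year is the same kind of event as the main component of the endpoint, and the peptide level is a plausible marker of risk. Whatever such variables explain, if left out of a negative binomial model, stays in the dispersion K, and K enters the variance of the log rate ratio directly. SAP 4.1 says the data were insufficient to estimate dispersion: "For this sample size calculation, a dispersion factor (K) of 1 was assumed". Adjustment can therefore narrow the confidence interval of the primary rate ratio with no extra patient, visit or assay. With a log link and randomised treatment, it leaves the rate ratio being estimated essentially unchanged. SAP Section 5 already moves age from categorical to continuous to gain precision, so the rationale is one the SAP accepts.

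**Working it through.** **Inputs from the documents.** SAP 4.1: "Assuming a rate of recurrent HF hospitalisation or CV death of 0.7 events/year in the placebo group"; "to demonstrate a statistically significant rate ratio of 0.75"; "with a power of 80% and a 2-sided alpha of 0.05"; K = 1; 500 per arm. Protocol synopsis: mean follow-up of 11 months, so T = 11/12 year.

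**The plan's own figure.** The Zhu-Lakkis formula is n per arm = [1.96√V0 + 0.8416√V1]² / (ln 0.75)².
- V1 = (1/0.7 + 1/0.525)/(11/12) + 2×1 = 3.636 + 2 = 5.636.
- V0 at the reference rate = (2/0.7)/(11/12) + 2 = 5.117.
- n = 499.8, that is 500 per arm, with power 80.0%.

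The stated 1,000 is reproduced with no covariate gain counted. 1,000/0.91 = 1,099 matches the planned 1,100.

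**Baseline for the comparison.** A plain Wald calculation uses V1 throughout: Φ(0.2877×√(500/5.636) − 1.96) = 77.3%. This differs from 80.0% only in how the null variance is taken.

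**Assumed prognostic effects (none are in the documents).** 40% have a prior admission; the two covariates are independent of each other and of those already in the model.

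| | Lower | Upper |
|---|---|---|
| Rate ratio, prior admission | 1.5 | 2.0 |
| Peptide tertile multipliers | 1/1.25/1.6 | 1/1.5/2.25 |
| Squared CV, prior admission | 0.042 | 0.122 |
| Squared CV, peptide | 0.037 | 0.105 |

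**Residual dispersion.** Hold marginal K at 1: 1 + K_res = 2/[(1 + CV²prior)(1 + CV²peptide)]. K_res is 0.852 (lower) and 0.612 (upper).

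**Adjusted variance.** Once the covariates are in the model, subjects have different means μ, so information per subject in each arm is E[μ/(1 + K_res μ)], averaged over the six covariate cells.
- Lower: 0.4076 (placebo) and 0.3359 (FCM). Variance = 1/0.4076 + 1/0.3359 = 5.430, a fall of 3.7%. Power 78.8%. Patient equivalent 5.636/5.430 − 1 = 3.8%.
- Upper: 0.4401 and 0.3572. Variance = 5.072, a fall of 10.0%. Power 81.5%. Patient equivalent 5.636/5.072 − 1 = 11.1%.
- Weak effects (rate ratio 1.2; tertiles 1/1.1/1.2): variance 5.599, a fall of 0.7%. Power 77.6%, a gain of about 0.3 points.

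**Simulation with a different set of assumptions** (500 per arm, 1,200 trials; half with a prior admission at rate ratio 1.8; 1.28 per SD of log peptide). The mean standard error fell from 0.1055 to 0.1026 and Wald power rose from 78.1% to 79.9%. The mean log rate ratio was −0.2923 unadjusted and −0.2921 adjusted. Under no effect, the adjusted two-sided rejection rate was 4.6%.

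**The case against.** Adjusting for the allocation factors is coherent, was pre-specified in the protocol and is carried into the SAP. The exploratory models of SAP 4.6.3 will also show each omitted variable alongside treatment. That stands as a reason to treat this as an improvement and not a fault. The exploratory models, however, take one variable at a time with an interaction and do not feed the primary p-value.

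The prognostic strength is assumed. This stands: no section gives an effect for either variable, so calling them strong predictors would go beyond the documents. HF duration is already in the model, and newly diagnosed patients would not normally have a previous AHF admission, so part of the gain is already taken.

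A reader might infer a larger gain by putting K_res straight into 3.636 + 2K. That gives variance falls of 5% to 14% and power of about 80% to 83%. It treats every subject as still having the average rate, which overstates the gain.

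Adding covariates can also lose subjects. SAP 4.2.8 makes no substitution for missing values in general, and SAP Appendix I removes subjects whose peptide criterion was not confirmed from the PP set only. An FAS subject with no peptide value would drop out of the fitted model. This stands and must be dealt with in the change.

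Finally, the argument that the estimand is unchanged covers the rate ratio but not the Cox hazard ratio, which is not collapsible.

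**Conclusion.** The point holds as a cheap improvement. Under the assumed effects, the primary model forgoes a variance reduction of about 4% to 10%, or roughly 1.5 to 4 points of power at K = 1. The gain is near 0.3 points if the effects are weak and zero if there are none, and overlap with HF duration would lower it further.

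A reader might take the 77.3% baseline to mean that the trial is underpowered and that these covariates repair it. The documents do not support that: 80% at 500 per arm reproduces under the cited formula and stated inputs with no allowance for covariates. Nothing in the current adjustment set is invalid.

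**What to change.** Before unblinding:
- Add AHF hospitalisation in the previous 12 months (yes/no) and the SAP 4.2.6 within-assay peptide tertile as main effects to the primary and secondary negative binomial models, keeping the present covariates.
- State a rule that keeps every FAS subject in the model, for example a separate category for a missing peptide or prior-admission value.
- Keep the model with minimisation factors only as a sensitivity analysis.
- Record the change in SAP Section 5.
- If the Cox models are changed as well, state that their hazard ratios become conditional on the added covariates.

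The cost is SAP wording and three more parameters (one for prior admission, two for tertiles), plus one for each missing category used. No new data are needed.
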